9.1. Primary Efficacy Endpoint and Analysis

The primary endpoint in this study is the percentage change in EASI score from Baseline at Week 16.

The primary endpoint (primary analysis) will be analyzed using analysis of covariance (ANCOVA) with treatment group as factor and Baseline EASI as covariate. Each active treatment dose will be compared with placebo. No adjustment for multiplicity will be made and the 0.05 level of significance will be used to claim efficacy compared with placebo. Least square means and the 95% confidence interval of the difference between each active treatment and placebo will be calculated.

The primary analysis set will be the ITT population with multiple imputation approach to handle missing values. The same analyses will be repeated for Weeks 20, 12, 8, 4 and 2. These analyses will be repeated on the PP population.

LS Mean (+/-SE) percentage change of EASI score will be presented graphically over time from Baseline to Week 2, 4, 8, 12, 16, and 20.

Actual values, change from baseline values, and percentage change from baseline of EASI will be summarized by visit using descriptive statistics and presented graphically over time.

The mixed model for repeated measures (MMRM) will be used as a supportive analysis with data collected after date of first disallowed medication 'treated as missing'. If disallowed medication is introduced the same day as an efficacy assessment, the efficacy assessment will be used as is. Some patients may not have any post-baseline data collected before initiation of disallowed medication. To ensure that all patients are included in the analysis, the baseline value for these patients should be carried forward as the first post-baseline assessment, corresponding to imputing a change of 0 at the first post-baseline assessment. The MMRM model will be implemented using SAS PROC MIXED with treatment group, visit, and treatment-by-visit interaction as factors and baseline EASI score by-visit interaction as a covariate. A restricted maximum likelihood (REML) will be used. The Kenward-Roger approximation will be used to estimate the denominator degrees of freedom and adjust standard errors. Least Squares Means Estimates and 95% confidence intervals will be given for each treatment group and for the difference between treatment groups (here also p-values will be presented). As an additional supportive analysis, this MMRM analysis will be repeated, with all observed data included irrespectively of disallowed medication or discontinuation of study drug.

EASI (including change from baseline values, percentage change from baseline values, EASI50, EASI75, and EASI90) will be listed.

9.2. Secondary Efficacy Endpoints and Analyses

Continuous secondary efficacy endpoints will be analyzed based on observed data prior to first initiation of disallowed medication using MMRM, using a modelling approach assuming MAR for missing data. If disallowed medication is introduced the same day as an efficacy assessment, the efficacy assessment will be used as is.

The binary secondary efficacy endpoints will be analyzed using difference in proportions, comparing each active treatment group to placebo in the ITT population with handling of missing data and data 'treated as missing' as specified in Section 9. Response by treatment group and difference in response rate and p-values compared to placebo will be presented.

The secondary endpoints and the percentage change of BSA will be presented graphically over time from Baseline to Week 20. In addition, shift tables will be provided between Baseline and each visit for the IGA-AD distribution. The EASI percentage changes from Baseline will be plotted to identify where the best separation between treatments occur. These figures and tables are based on observed cases, thus purely descriptive.

9.2.1. Key Secondary Endpoints

- Patients achieving 75% reduction in EASI (EASI75) response at Week 16.
- Patients achieving a score of Clear (0) or Almost Clear (1) and an at least 2-point improvement in IGA-AD at Week 16.

In addition to absolute EASI scores, response to treatment is presented as a percentage response rate: EASI50, EASI75, and EASI90. EASI75 represents the percentage of patients who have achieved a 75% or more reduction in their EASI score from baseline.

The key secondary endpoints (primary analysis) will be analyzed using difference in proportions, comparing each active treatment group to placebo in the ITT population. Response by treatment group and difference in response rate and p-values compared to placebo will be presented. These analyses will be repeated on the PP population. As supportive analysis, this analysis will be repeated, with handling of missing data and data 'treated as missing' as non-response. As an additional supportive analysis, for both key secondary endpoints, this analysis will be repeated with all observed data included irrespectively of disallowed medication or discontinuation of study treatment. Any other missing data should be imputed as non-response. In case of imbalance in baseline disease severity between treatment groups an additional supportive analysis stratifying for baseline IGA using a Cochran-Mantel-Haenszel (CMH) test will be repeated (in a descriptive table and a table using non-response imputation if a score is missing or 'treated as missing') by subgroups: baseline IGA (moderate / severe), body weight at baseline(<80, 80-100, ≥100 kg) and region (US vs non-US).

Actual values of IGA-AD will be summarized by visit using descriptive statistics and presented graphically over time. The percentage of patients with EASI75 and the percentage of patients achieving clear (0) or almost clear(1) will be presented graphically over time. These figures are based on observed cases, thus purely descriptive.

9.2.2. Other Secondary Endpoints

- Patients achieving a score of clear (0) or almost clear (1) and at least a 2-point improvement in IGA-AD at Weeks 2, 4, 8, 12, and 20.
- Patients achieving EASI75 at Weeks 2, 4, 8, 12, and 20.
- Patients achieving EASI50 and EASI90 response at Weeks 2, 4, 8, 12, 16, and 20.
- Percent change from Baseline in EASI at Weeks 2, 4, 8, 12, and 20.
- Change from Baseline in the peak pruritus NRS score at Weeks 1, 2, 4, 8, 12, 16, and 20.
- Patients achieving at least a 4-point improvement in the peak pruritus NRS from baseline at Weeks 1, 2, 4, 8, 12, 16, and 20 among patients with a baseline score ≥4.
- Change from Baseline in affected BSA at Weeks 2, 4, 8, 12, 16, and 20.
- Change from Baseline in DLQI score at Weeks 8, 16, and 20.
- Change from Baseline in POEM score at Weeks 2, 4, 8, 12, 16, and 20.
- Change from Baseline in PGIS score at Weeks 2, 4, 8, 12, 16, and 20.
- PGIC score at Weeks 2, 4, 8, 12, 16, and 20.
- Change from Baseline in sleep disturbance NRS score at Weeks 1, 2, 4, 8, 12, 16, and 20.
- Change from Baseline in skin pain NRS score at Weeks 1, 2, 4, 8, 12, 16, and 20.

EASI50 represents the percentage of patients who have achieved a 50% or more reduction in their EASI score from baseline. EASI90 represents the percentage of patients who have achieved a 90% or more reduction in their EASI score from baseline.

Continuous secondary efficacy endpoints will be analyzed using MMRM, similar to the supportive MMRM for the primary endpoint, i.e. based on observed data prior to first initiation of disallowed medication.

The analysis on categorical secondary efficacy endpoints will be performed using difference in proprotions, comparing each active treatment group to placebo in the ITT population with handling of missing data and data 'treated as missing' as specified in Section 9. Response by treatment group and difference in response rate and p-values compared to placebo will be presented.

Actual values and change from baseline values of POEM, PGIS, sleep disturbance NRS and skin pain NRS will be summarized by visit using descriptive statistics and presented graphically over time. Actual values of PGIC will be summarized by visit using descriptive statistics and presented graphically over time. Actual values, change from baseline values and percentage change from baseline of BSA and DLQI will be summarized by visit using descriptive statistics and presented graphically over time. The percentage of patients with EASI50 and EASI90 will be presented graphically over time. These tables and figures are based on observed cases, thus purely descriptive. In addition a summary table presenting patients achieving reduction of DLQI score of ≥4 points at week 16 from baseline in patients in the ITT population with a baseline score ≥4 will be provided.

POEM, PGIS, peak pruritis NRS, sleep disturbance NRS and skin pain NRS (including change from baseline values) will be listed. PGIC will be listed. BSA and DLQI (including change from baseline and percentage change from baseline values) will be listed.

9.2.3. Exploratory Endpoints

- Patients achieving at least a 2-point improvement in the peak pruritus NRS from baseline at Weeks 1, 2, 4, 8, 12, 16, and 20 among patients with a baseline score ≥4.
- Change from Baseline in pulmonary status NRS in patients with asthma at Weeks 4, 8, 12, 16, and 20.
- Patients achieving 100% reduction in EASI (EASI100) response at Weeks 2, 4, 8, 12, 16, and 20

All exploratory endpoints will be summarized descriptively in the ITT Population. A summary table of patients achieving EASI50, EASI75, EASI90, EASI100 and IGA 0/1 response at weeks 2, 4, 8, 12, 16 and 20 will be provided. Peak pruritus NRS, pulmonary status NRS will be listed.

10. Pharmacokinetics

Exploratory endpoint: Plasma levels of the drug and its metabolites at Weeks 4, 8, and 16.

Blood samples will be collected for measurement of concentrations of orismilast and its major metabolites (LEO 40815 and LEO 32728) as specified in the SoA in Protocol Section 9 before the morning dose of the study drug. The concentration of study drug will be determined from the plasma samples using a validated analytical method.

Blood sampling for measuring plasma levels: The patients will be instructed to self-administer the study drug approximately 12 hours prior to the planned blood collection for PK analysis. The date and time of the dose taken prior to the PK blood sampling will be collected and registered.

Blood sampling for calculation of PK profiles: In addition to the sample collected for measuring trough levels, patients will be offered optional participation in specific blood sampling for calculation of PK profiles. This additional procedure is voluntary for patients and patient's consent will be obtained before collection of the blood samples. For PK profiling, 4 or 5 additional blood samples will be collected during each visit at Week 4 and Week 16. The patient will be instructed to take the next dose of the study drug in the clinic and blood samples will be taken at the following timepoints: 45 min, 2.5 hours (estimated C_{max}), 4 hours and 6 hours after intake of the study drug, as shown in the figure below. An additional optional 8-hour blood sample will be collected if the patient agrees. The actual date and time of the study drug administration in the clinic and each blood sample collection will be recorded.

Figure 2 Pharmacokinetic Blood Sample Collection

Abbreviations: H, hour; Lab, laboratory; PK, pharmacokinetic

The plasma levels of the drug and its metabolites will be summarized descriptively by visit and time categories: 'before 12 hours', 'at 12 hours (+/- 15%), 'after 12 hours'.

A listing of PK levels will be presented by treatment group, subject number, and collection date and time.

11. Pharmacodynamics

Exploratory endpoint: Change from Baseline in skin biomarkers at Week 16 collected via tape stripping and analyzed using proteomic methods.

Stratum corneum skin samples will be collected using the tape stripping method to evaluate biomarker expression levels. Tape stripping is a minimally invasive, nonscarring approach utilizing serial adhesive films to capture the stratum corneum and the upper part of the granular layer. At Baseline, before administration of study drug, 1 lesional and 1 nonlesional area will be identified, and 20 consecutive skin samples will be collected from each area. At Week 16, the same procedure will be repeated only from the same lesional area sampled at Baseline. Details of stratum corneum skin samples' storage, and shipping procedures are provided in a separate laboratory manual. Change from Baseline in skin biomarkers will be summarized descriptively.

A listing of skin biomarker results will be presented by treatment group, subject number, and collection date and time.

12. Safety

All safety analyses will be conducted using the safety population.

Safety will be assessed based on adverse event (AE) reports, physical examination, vital signs, ECGs, clinical laboratory data, HADS, and C-SSRS using descriptive statistics.

No inferential statistical analyses are planned on the safety parameters of this study.

12.1. Adverse Events

AEs for all patients in the safety population will be included in the AE summaries.

Adverse events will be summarized by system organ class (SOC) and preferred term (PT) for each treatment and Orismilast total, based on the MedDRA dictionary version 24.0. Severity of AEs will be graded according to National Cancer Institute (NCI) Common Terminology Criteria for Adverse Events (CTCAE) version 5.

Any AEs that occur before dosing on study Baseline will be categorized as pretreatment events. TEAEs will be defined as those AEs that occur or worsen in severity after initial dosing and up to 7 days after the last dose of study drug.

Duration will be calculated for AEs that resolve as the difference between the resolution date and onset date plus 1 and expressed in days.

The summary tables will include the number of patients and the number of events. Percentages will be based on the number of patients in the safety population. For summaries by SOC and PT, a patient will be counted once at the SOC level and once at each PT within the SOC level.

For summaries by SOC, PT, and maximum severity, a patient will be counted once at the highest severity level for which the event occurred at the SOC level and the highest severity level for each unique PT within that SOC level. Therefore, patients may only contribute once to each PT and once to each SOC level.

The summaries presenting frequency of AEs by SOC and PT will be ordered by Orismilast total descending frequency of SOC and then, within a SOC, by Orismilast total descending frequency of PT.

The following tables will be provided:

- An overall summary of the number of events and number and percentage of patients reporting TEAEs, related TEAEs (TEAEs recorded as "Relationship to study drug" = "Possibly" or Probably" or "Definitely"), serious TEAEs (TESAEs), TEAEs resulting in death, TEAEs of special interest, TEAEs leading to study drug discontinuation, TESAEs leading to study drug discontinuation, TEAEs by relationship and TEAEs by toxicity grade (including exposure adjusted incidence rates [EAIR]);.A similar summary will be presented starting within the dose titration period (initial 3 weeks)." (without EAIR).
- TEAEs overall by system organ class and preferred term (including EAIR);
- TEAEs overall by system organ class and preferred term starting within the dose titration period (initial 3 weeks)
- TEAEs by maximum toxicity grade, overall and by system organ class and preferred term;
- TEAEs by toxicity grade, overall and by system organ class and preferred term;

- TEAEs by maximum relationship to study medication, overall and by system organ class and preferred term;
- TEAEs by relationship to study medication, overall and by system organ class and preferred term;
- TEAEs leading to study drug discontinuation, overall and by system organ class and preferred term;
- TEAEs leading to study drug discontinuation, overall and by body weight at baseline system organ class and preferred term;
- TEAEs leading to study drug discontinuation, overall and by region, system organ class and preferred term; TEAE coded by MedDRA preferred term as diarrhoea, nausea, headache, dizziness and vomiting by time of onset of event;
- TEAEs of special interest, overall and by system organ class and preferred term;
- AEs starting in the 4-week Follow-up period overall by system organ class and preferred term;
- SAEs starting in the 4-week Follow-up period overall and by system organ class and preferred term;

Only TEAEs will be included in the summary tables, however separate listings for treatment-emergent AEs, non-treatment-emergent AEs, AEs starting within the dose titration period (initial 3 weeks), and AEs starting in the 4-week Follow-up period will be generated. Additional listings will be provided for deaths, AESIs, serious AEs, and AEs Leading to Study Drug Discontinuation.

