### 5.2.3 Safety Endpoints

The safety endpoints of this study are as follows:

- The occurrence, severity, and seriousness of treatment-emergent AEs (TEAEs) reported over the 16-week Treatment Period and the 4-week Follow-up Period
- Changes from Baseline in physical examination findings; vital signs measurements (body temperature, respiration rate, heart rate, and systolic and diastolic blood pressure measurements); and body weight over the 16-week Treatment Period and the 4-Week Follow-up Period
- Clinically significant abnormal changes in ECG findings over the 16-week Treatment Period
- Changes from Baseline in safety laboratory values (hematology, serum chemistry, and urinalysis) over the 16-week Treatment Period
- Change from Baseline in HADS score at each visit except Week 1
- C-SSRS score at each visit except Week 1

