## 11.8.1 Adverse Events

An AE is any symptom, physical sign, syndrome, or disease that either emerges during the study or, if present at screening, worsens during the study, regardless of the suspected cause of the event. All medical and psychiatric conditions (except those related to the indication under study) present at screening will be documented in the medical history eCRF. Changes in these conditions and new symptoms, physical signs, syndromes, or diseases should be noted on the AE eCRF during the rest of the study. Clinically significant laboratory abnormalities should also be recorded as AEs. Surgical procedures that were planned before the patient enrolled in the study are not considered AEs if the conditions were known before study inclusion; the medical condition should be reported in the patient's medical history.

Any AEs that occur before dosing at Baseline will be categorized as pretreatment events. TEAEs will be defined as those AEs that occur or worsen in severity after initial dosing and up to 7 days after the last dose of study drug.

Patients will be instructed to report AEs at each study visit. All AEs are to be followed up until resolution or a stable clinical endpoint is reached.

Each AE is to be documented on the eCRF with reference to date of onset, duration, frequency, severity, relationship to study drug, action taken with study drug, treatment of event, and outcome. Furthermore, each AE is to be classified as being serious or nonserious. Changes in AEs and resolution dates are to be documented on the eCRF.

For the purposes of this study, the period of observation for collection of AEs extends from the time the patient gives informed consent until the follow-up visit. Follow-up of the AE, even after the date of therapy discontinuation, is required if the AE persists until the event resolves or stabilizes at a level acceptable to the investigator.

When changes in the intensity of an AE occur more frequently than once a day, the maximum intensity for the event should be noted. If the intensity category changes over a number of days, then those changes should be recorded separately (with distinct onset dates).

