5.5. Safety Endpoints

• The occurrence, severity, and seriousness of treatment-emergent AEs (TEAEs) reported over the 16week Treatment Period and the 4-week Follow-up Period.

- Changes from Baseline in physical examination findings; vital signs measurements (body temperature, respiration rate, heart rate, and systolic and diastolic blood pressure measurements); and body weight over the 16-week Treatment Period and the 4-Week Follow-up Period.
- Clinically significant abnormal changes in ECG findings over the 16-week Treatment Period.
- Changes from Baseline in safety laboratory values (hematology, serum chemistry, and urinalysis) over the 16-week Treatment Period.
- Change from Baseline in HADS score at each visit except Week 1.
- C-SSRS score at each visit except Week 1.

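### TEAEs end 7 days after the last dose although the safety endpoint runs through the 4-week follow-up, so later-onset events have no severity, relationship or AESI table

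*SAP*

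**What the plan says.** Protocol 5.2.3 gives the first safety endpoint as "The occurrence, severity, and seriousness of treatment-emergent AEs (TEAEs) reported over the 16-week Treatment Period and the 4-week Follow-up Period". SAP 5.5 repeats it.

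Protocol 11.8.1 defines treatment-emergent events as those that "occur or worsen in severity after initial dosing and up to 7 days after the last dose of study drug", and SAP 12.1 uses the same window, "up to 7 days after the last dose of study drug". AE collection runs longer: "the period of observation for collection of AEs extends from the time the patient gives informed consent until the follow-up visit".

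In SAP 12.1 the tables by toxicity grade, maximum grade, relationship, maximum relationship and special interest are all for TEAEs. Two further items cover AEs and SAEs that start in the 4-week follow-up, each by SOC and PT. The same section then states "Only TEAEs will be included in the summary tables" and sends other events to listings. The SAP table index has Table 14.3.1.13 for follow-up AEs but shows no follow-up SAE table.

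Protocol 14.4 plans summaries of reported AEs by SOC and PT, by severity and by relationship, without limiting them to TEAEs. SAP section 14, on changes from the protocol, does not mention the narrowing.

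Under protocol 7.4, a patient who stops drug early has a follow-up visit within 4 weeks of the last dose and, if it is safe, is then offered to remain off treatment and attend the planned visits. SAP 7.2 defines the treatment period but not the follow-up period.

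**The concern.** The endpoint names a period that its own event definition mostly leaves out. Severity is one of the three things the endpoint asks for, and for events starting more than 7 days after the last dose no planned table shows it.

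Follow-up is part of the safety assessment here: protocol 6.3 sets it up for efficacy, safety and rebound. HADS, C-SSRS and weight are all measured at Week 20. A positive C-SSRS ideation answer or a HADS score of 15 or more is an AESI under protocol 11.8.2, but one that starts after day 7 is not in the table of TEAEs of special interest. Protocol 11.2 asks for a weight loss of at least 5% to be reported as a TEAE, yet a loss that first arises after day 7 is not one under protocol 11.8.1. Depression and weight loss are the class effects that protocol 4.3.2 says will be monitored.

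For patients who stop early and stay, the gap may be wider: without a definition of their follow-up period, some events may appear only in listings.

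**Working it through.** The plan states no figure for this point, so the check is a comparison of definitions followed by arithmetic on days.

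**Inputs.** TEAE window: 7 days after last dose (protocol 11.8.1, SAP 12.1). Follow-up: 4 weeks = 28 days, with a Week 20 visit window of ±3 days (protocol Table 4). Early stoppers may stay to Week 20 (protocol 7.4).

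**Where an event starting on days 8 to 28 is reported (patient who completes treatment)**

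| Attribute | In a planned table? | Source |
|---|---|---|
| Occurrence | Yes, by SOC and PT | SAP 12.1, Table 14.3.1.13 |
| Seriousness | Yes, by SOC and PT; table not in the index | SAP 12.1 |
| Severity | No; listing only | SAP 12.1 |
| Relationship | No; listing only | SAP 12.1 |
| AESI status | No; listing only | SAP 12.1 |

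**Share of follow-up time outside the window.** (28 − 7)/28 = 21/28 = 75%. With the visit at 25 days, 18/25 = 72%; at 31 days, 24/31 = 77%.

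**Share of follow-up events outside it.** The documents give no event counts, so this needs an assumption. Suppose the onset rate falls with half-life h days after the last dose. Then

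share = (2^(−7/h) − 2^(−28/h)) / (1 − 2^(−28/h)).

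| Assumed onset | Share after day 7 |
|---|---|
| Uniform | 75% |
| h = 28 days | 68% |
| h = 14 days | 61% |
| h = 7 days | 47% |
| h = 3.5 days | 25% |

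For h = 7: (0.5 − 0.0625)/(1 − 0.0625) = 0.467. The share passes one half only when h is longer than about 8 days.

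**Early stoppers who stay to Week 20.** If drug stops at week w, the share of off-drug time outside the window is (20 − w − 1)/(20 − w): 7/8 = 87.5% for w = 12, 15/16 = 94% for w = 4, and 17/18 = 94% for w = 2.

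Take w = 4, where TEAEs end at Week 5. If follow-up means Weeks 16 to 20, events starting in Weeks 5 to 16 (11 of the 16 off-drug weeks) enter no summary table. If it means the 4 weeks after stopping, any events recorded in Weeks 8 to 20 (12 of 16 weeks) enter none. The SAP does not say which reading applies.

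**The case against.** The strongest reply is that the endpoint uses a term the protocol itself defines. Read with protocol 11.8.1, it means 7-day TEAEs reported up to Week 20, and that can be produced. This reading removes the verbal conflict. It does not supply a severity table for later onsets, the summaries planned in protocol 14.4, or a rule for early stoppers.

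The 7-day window is also defensible. The modified-release tablet has a half-life of about 6.5 hours (protocol 4.4.1), and estimates reach 10 hours at 60 mg BID (protocol 4.2.2.1). Seven days is 168 hours, so about 17 to 26 half-lives. This supports an on-treatment window of that length, but not an endpoint worded to run four weeks.

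Three stronger readings are tempting, and the documents do not support them.

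- A reader might infer that the safety endpoint cannot be produced at all. Occurrence and seriousness of follow-up events do have planned tables. Severity is the component that is missing.
- A reader might take 75% as the share of events lost. It is a share of time, and the events themselves remain in listings.
- A reader might conclude that psychiatric signals vanish. HADS categories, including 15 to 21, are tabulated at each visit (SAP 12.6), C-SSRS ideation has a shift table to all post-baseline visits (SAP 12.7), and AESIs, SAEs and deaths are listed. What is lost is their place in the AESI table.

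Relatedness is not part of the endpoint; the case for tabulating it rests on protocol 14.4.

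It is also unclear whether AEs are collected from early stoppers after their own follow-up visit, since collection ends at that visit. The early-stopper gap is therefore possible, not certain. The sentence limiting tables to TEAEs can be read as qualified by the follow-up tables listed just before it, and the missing index row is a small matter because the text plans the table.

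**Conclusion.** The point holds as a mismatch between endpoint, event definition and table list. Following the plan leaves the severity component of the endpoint untabulated for events starting more than 7 days after the last dose. It also leaves out relationship, which protocol 14.4 plans to summarise, and AESI status. The affected period is 21 of 28 follow-up days for a patient who completes treatment (72% to 77% over the visit window). The number of events affected is unknown: under the onset patterns tried, between a quarter and three quarters of follow-up events.

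For early stoppers who remain in the trial, some off-drug events may reach no summary table. That depends on how follow-up is defined for them and on whether AEs are still collected after their follow-up visit.

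Safety is analysed descriptively, so no test or error rate is affected. The repair is cheap and should be made before unblinding.

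**What to change.** Choose one of two routes before unblinding.

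- **(a) Extend the flag.** Define TEAEs in protocol 11.8.1 and SAP 12.1 as onset or worsening from first dose to the patient's last study visit. Keep a labelled subset for events up to 7 days after the last dose, and base the exposure-adjusted incidence rates on that subset so that off-drug events do not enter them.
- **(b) Keep 7 days.** Reword the endpoint in protocol 5.2.3 and SAP 5.5 to cover TEAEs and also AEs starting in follow-up. Produce the follow-up and post-treatment AE tables, including AESIs, by CTCAE grade and by relationship. State in protocol 11.2 how a weight loss first arising after day 7 is classified.

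Under either route:

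- define the post-treatment period for early stoppers as more than 7 days after the last dose through the last study visit, and confirm that AEs are collected throughout it;
- add the follow-up SAE table to the SAP index;
- correct the SAP 12.1 sentence that limits summary tables to TEAEs.

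Either route brings the uncovered share of follow-up to zero. The cost is protocol and SAP wording, a changed or added flag in the AE dataset and a few more tables. The downside is that some background events arising off drug will be counted; the 7-day subset in (a), or the separate tables in (b), keep them distinguishable.
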